7.2 Exclusion Criteria

- 1. History or presence of any other major neurological disease
- 2. Any seizures in the prior 3 months
- 3. The presence of contracture at any joints that would interfere with interpretation of any of the neurological assessments (*e.g.*, contracture preventing the detection of any increase in the range of motion or ability to perform a task)
- 4. Other neurologic, neuromuscular or orthopedic disease that limits motor function
- 5. Clinically significant finding on MRI of brain not related to TBI
- 6. Known presence of any malignancy except squamous or basal cell carcinoma of the skin
- 7. History of CNS malignancy
- 8. Positive findings on tests for occult malignancy, unless a non-malignant etiology is confirmed

- 9. Uncontrolled systemic illness, including, but not limited to: hypertension (systolic >150 mm Hg or diastolic >95 mm Hg); diabetes; renal, hepatic, or cardiac failure
- 10. Uncontrolled major psychiatric illness, including depression symptoms (CESD-R Scale of ≥16)
- 11. Total bilirubin >1.9 mg/dL
- 12. Serum creatinine >1.5 mg/dL
- 13. Hemoglobin <10.0 g/dL
- 14. Absolute neutrophil count <2000/mm³
- 15. Absolute lymphocytes <800/mm³
- 16. Platelet count $<100,000/\text{mm}^3$
- 17. Liver disease documented by AST (SGOT) or ALT (SGPT) ≥2.5 x institutional upper limit of normal
- 18. Serum calcium >11.5 mg/dl
- 19. Unexplained abnormal preoperative test values (blood tests, electrocardiogram [ECG], chest X-ray); x-ray evidence of infection; uncontrolled atrial fibrillation or uncontrolled congestive heart failure
- 20. Presence of craniectomy (without bone flap replacement) or other contraindication to stereotactic surgery
- 21. Participation in any other investigational trial within 4 weeks of initial screening or within 7 weeks of study entry
- 22. Botulinum toxin injection, phenol injection, intrathecal baclofen, or any other interventional treatments for spasticity (except bracing and splinting) within 16 weeks of the Baseline visit. (interventional treatment refers to treatment done with special equipment which is typically performed in a surgical or procedural type facility this does not apply to oral medications such as oral baclofen).
- 23. Ongoing use of herbal or other non-traditional drugs
- 24. Substance use disorder (per DSM-V criteria, including drug or alcohol)
- 25. Contraindications to head CT or MRI
- 26. Pregnant or lactating
- 27. Female patients of childbearing potential unwilling to use an adequate birth control method during the 12 months of the study
- 28. Any other condition or situation that the investigator believes may interfere with the safety of the subject or the intent and conduct of the study
- 29. Patients with allergic reactions to the ingredients of SB623, the drugs used when administering SB623 or the drugs used in testing (applicable to Japan only)

8.0 INVESTIGATIONAL PLAN

8.1 Overall Study Design

This is a double-blind, sham-surgery controlled study of stereotactic, intracranial injection of SB623 cells in patients with fixed motor deficits from TBI. The study will be conducted at approximately 30 sites in North America (i.e., US), Eastern Europe (i.e., Russia and Ukraine), and Asia Pacific (i.e., Japan).

Two groups, Group 1 and Group 2, will receive SB623 and sham surgery, respectively, in a 3:1 randomization scheme. Group 1 will be further randomized in a 1:1:1 ratio to receive either 2.5, 5 million or 10 million SB623 cells. Randomization will be performed via an interactive web response system (IWRS). For subjects enrolled outside of Japan, the randomization will be stratified by GOS-E score (i.e. scores 3, 4, 5 or 6); for subjects in Japan, the randomization will not be stratified.

The study schematic is shown in the figure below.

Figure 4 Study Schematic

6 months to primary endpoint 6 month followup

The neurological assessment team evaluating Fugl-Meyer Motor Score and other efficacy endpoints will be blinded, with the subjects also blinded. The surgical team will remain unblinded, any communication between the surgical and neurological team (including the investigator) will be blinded.

Safety will be monitored by the Investigator, Principal Monitor, Medical Monitor (Unblinded and Blinded), and an external Data Safety Monitoring Board including clinical symptoms, laboratory findings, and head MRI. Two or more serious adverse events potentially attributed to SB623 as assessed by the Investigator will trigger a review by the DSMB before continuing enrollment. In addition, the DSMB will review the study at 25%, 50%, 75% and 100% enrollment. The DSMB shall be the final arbitrator for attributions. Efficacy will be determined based on changes in the clinical measures of TBI through standardized assessments (Fugl-Meyer Motor Scale (FMMS), Disability Rating Scale (DRS), Action Research Arm Test (ARAT), Gait Velocity, two Domains of the NeuroQOL and the Global Perception of Change (subject and clinician). MRI of the brain **Protocol TBI-01 Version 5, May 17, 2018**

SanBio, Inc.

Confidential and Proprietary

will be performed at scheduled time points and imaging (pre- and post-contrast T1-weighted, dual echo, and FLAIR sequences). MRIs will be analyzed by a central reader and post-surgery blinded reports will be sent back to the assessment site staff (excluding the assessment site efficacy assessor) without any accompanying images. Exploratory imaging (e.g. diffusion tensor imaging [DTI] and dynamic susceptibility contrast [DSC] MRI for perfusion imaging) will also be performed. Note that in this document DSC and Perfusion Imaging are used interchangeably. Primary and secondary efficacy assessments will be completed solely by blinded study personnel (i.e. assessment site efficacy assessor) that do not have access to patient study safety information (this includes adverse events, concomitant medications, progress notes, MRI reports, etc.).

Stopping Rules:

If the DSMB determines that continuation of enrollment in the trial provides an unreasonable risk to the patients, it may recommend study termination. All SAEs, regardless of attribution shall be reviewed by the DSMB.

In addition, adverse events attributable to the surgical procedure, such as intracranial infection, intracranial bleeding and seizures, shall be subject to review by the DSMB.

The DSMB shall be the final arbitrator for attributions.

8.2 Duration of Patient Participation

Twelve months post-surgery (except if there is an unresolved adverse event of at least Grade 2 and at least possibly related to the therapy, in which case the patient will be followed until resolved or reduced to Grade 1).

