	Details for preparation of the cell suspension for administration and for loading the syringe in the OR will be provided by the Sponsor in a separate document. Clinical sites will be provided necessary materials for reconstitution of the cells and will be trained by the Sponsor. The cryopreserved cells will be thawed, washed, centrifuged, and re- suspended in Plasma-Lyte A at varying concentrations for administration to the patient within approximately 3 hours of dose release. Prior to administration, a gram stain and a test for endotoxin will be done and a sterility test initiated on the last cell wash to ensure continued sterility. If the endotoxin level is > 5 EU/mL or the gram stain is positive, implantation will not occur. If the sterility test is positive, an investigation will be conducted to determine the source of the contamination by the sponsor. In addition, identification of the pathogen and sensitivity will be done and the patient treated with an appropriate antibiotic. In this event, the patient will be followed closely for adverse events associated with a possible infection and response to antimicrobial therapy, including frequent clinic visits until any infection is cleared.
	SB623 cells will be kept frozen in vapor phase liquid nitrogen or in storage equipment maintaining the same temperature as vapor phase liquid nitrogen, at study sites, either within the shipping or other acceptable storage container approved by the Sponsor until ready for use. SB623 cells will then be thawed, washed, and re-suspended in Plasma- Lyte A® at the concentration summarized above.
	Sites will be trained in proper cell handling procedures and these will be documented.
Duration of Patient Study Participation	Twelve months post-randomization (except if there is an unresolved adverse event, in which case the patient will be followed until the adverse event has resolved or a stable clinical endpoint has been reached).

Efficacy	Primary Efficacy Endpoint:						
Parameters	 Change from baseline in Fugl-Meyer Motor Scale (FMMS) score at Week 24 among all patients 						
	Secondary Efficacy Endpoints:						
	• Change from baseline in Disability Rating Scale (DRS) score at Week 24 among all patients						
	 Change from baseline in Action Research Arm Test (ARAT) total score at Week 24 among upper extremity deficit patients Change from baseline in Gait Velocity at Week 24 among lower extremity deficit patients 						

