16.2 Adverse Event Reporting Period

The adverse event reporting period for this trial begins upon Enrollment and ends 12 months after the administration of SB623.

All AEs (both serious and non-serious) and PTCs must be followed until resolution or until a stable clinical endpoint is reached. All measures required for AE management and the ultimate outcome of the AE must be recorded in the source document and reported to the Sponsor.

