16.3 Recording of AEs

All AEs, regardless of severity, seriousness, or presumed relationship to the study product or surgical procedure, must be recorded using medical terminology in the source document and on the CRF. Events will be recorded at all study sites using standard terminology provided by the Sponsor or designate (*e.g.*, CRO), such as MedDRA terminology.

The WHO (World Health Organization) Standard Toxicity Criteria (STC) will be used to assist in categorizing and grading adverse events. A copy of the WHO STC will be provided in the study documents. Whenever possible, a diagnosis should be given when signs and symptoms are due to common etiology (*e.g.*, cough, runny nose, sneezing, sore throat, and head congestion should be reported as "upper respiratory infection").

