16.4 Assessing Relationship of AE to Study Product or Surgical Procedure

The Investigator must record his/her opinion concerning the relationship of the AE to the study product and the surgical procedure on the Adverse Event CRF. Table 4 below provides guidance for assigning relationship to study product or surgical procedure.

	Surgical Procedure
Unrelated	No temporal relationship to study product or surgical procedure, or the presence of a reasonable causal relationship to another drug, concurrent disease, or circumstance and the adverse event (AE).
Unlikely	A temporal relationship to study product or surgical procedure, but no reasonable causal relationship between study product or surgical procedure and the AE.
Possibly	A reasonable causal relationship between the study product or surgical procedure and the AE. Information related to withdrawal of cell treatment/procedure was lacking or unclear.
Probably	A reasonable causal relationship between the study product or surgical procedure and the AE. The event responded to withdrawal of cell treatment/procedure. Re- challenge was not required.
Definitely	A reasonable causal relationship between the study product or surgical procedure and the AE. The event responded to withdrawal of the cell treatment/procedure, and recurred with re-challenge, when clinically feasible.

Table 4Relationship of Adverse Event to Administration of the Study Product or
Surgical Procedure

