16.6 Follow-up of Adverse Events

All AEs (both serious and non-serious) should be followed until resolution or until a stable clinical endpoint is reached. All measures required for AE management and the ultimate outcome of the AE must be recorded in the source document.

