Cardiac	Hypertension	none or no change	asymptomatic, transient increase by greater than 20 mm Hg (D) or to > 150 / 100 if previously WNL. No treatment required.	recurrent or persistent increase by greater than 20 mm HG (D) or to > 150 / 100 if previously WNL. No treatment required.		hypertensive crisis

Category	Toxicity	Grade 0	Grade 1	Grade 2	Grade 3	Grade 4
Cardiac	Hypotension	none or no change	changes requiring no therapy (including transient orthostatic hypo- tension)	requires fluid replacement or other therapy but not hospitalisation	requires therapy and hospitalisation; resolves within 48 hours of stopping the agent	requires therapy and hospitalisation for > 48 hrs after stopping the agent
Neurologic	Neuro: sensory	none or no change	mild paraesthesias; loss of deep tendon reflexes		severe objective sensory loss or paraesthesias that interfere with function	
Neurologic	Neuro: motor	none or no change	subjective weakness; no objective findings	mild objective weakness without significant impairment of function	objective weakness with impairment of function	paralysis
Neurologic	Neuro: cortical	none	mild somnolence or agitation	moderate somnolence or agitation	severe somnolence, (>50 % waking hours), agitation, confusion, disorientation or hallucinations	coma, seizures, toxic psychosis
Neurologic	Neuro: cerebellar	none	slight incoordination, dysdiadochokinesia	intention tremor, dysmetria, slurred speech, nystagmus	locomotor ataxia	cerebellar necrosis
Neurologic	Neuro: mood	no change	mild anxiety or depression	moderate anxiety or depression	severe anxiety or depression	suicidal ideation

Category	Toxicity	Grade 0	Grade 1	Grade 2	Grade 3	Grade 4
Neurologic	Neuro: headache	none	mild	moderate or severe but transient	unrelenting and severe	
Neurologic	Neuro: constipation	none or no change	mild	moderate	severe	ileus > 96 hrs
Neurologic	Neuro: hearing	none or no change	asymptomatic, hearing loss on audiometry only	tinnitus	hearing loss interfering with function but correctable with hearing aid	deafness not correctable
Neurologic	Neuro: vision	none or no change			symptomatic subtotal loss of vision	blindness
Pain	Pain	none	mild	moderate	severe	reg. narcotics
Skin	Skin	none or no change	scattered macular or papular eruption or erythema that is asymptomatic	scattered macular or papular eruption or erythema with pruritus or other associated symptoms	generalised symptomatic macular, papular or vesicular eruption	exfoliative dermatitis or ulcerating dermatitis

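### Section 8.2 ends follow-up at 12 months for some unresolved adverse events that the synopsis and section 16.2 require to be followed until resolved or stable

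*Protocol*

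**What the plan says.** Four places in the protocol govern what happens to a patient whose adverse event is still open at 12 months.

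- **Section 8.2 (Duration of Patient Participation)** ends participation 12 months after surgery. The exception is an "unresolved adverse event of at least Grade 2 and at least possibly related to the therapy"; in that case "the patient will be followed until resolved or reduced to Grade 1".
- **Synopsis, Duration of Patient Study Participation**, also sets 12 months, "except if there is an unresolved adverse event, in which case the patient will be followed until the adverse event has resolved" or has reached a stable clinical endpoint. It has no condition on grade or relatedness.
- **Section 16.2** states: "All AEs (both serious and non-serious) and PTCs must be followed until resolution or until a stable clinical endpoint is reached". It also asks for the ultimate outcome of each event to be recorded and reported to the sponsor.
- **Section 16.6** states: "All AEs (both serious and non-serious) should be followed until resolution or until a stable clinical endpoint is reached".

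Two other sections bear on the reading. Section 16.3 says that "All AEs, regardless of severity, seriousness, or presumed relationship to the study product or surgical procedure, must be recorded". Section 16.4 asks the investigator for an "opinion concerning the relationship of the AE to the study product and the surgical procedure", on a five-level scale running from Unrelated and Unlikely through Possibly and Probably to Definitely.

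**The concern.** Section 8.2 is where a site looks to decide when a patient leaves the study. It filters on grade and on relatedness, and the synopsis, 16.2 and 16.6 do neither. A site that closes patients out by 8.2 can stop following an event that 16.2 says must be followed, and nobody has to establish first that the event is stable.

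What would be lost is the eventual outcome of some late, open events after a single intracranial implantation of allogeneic cells. The relatedness filter makes this less comfortable. The investigator makes the judgement, assessment-site staff are blinded (section 11.0), and the DSMB is the final arbiter of attribution (section 14.0). Section 8.2 does not say whose attribution decides release.

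**Working it through.** No arithmetic applies; the point depends on no sample size, error rate or event count. The check is to apply each rule to the same event, unresolved at 12 months.

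| Event at or after 12 months | Section 8.2 | Synopsis, 16.2, 16.6 |
|---|---|---|
| Grade 1, any attribution, not stable | Released | Followed |
| Grade 2 or higher, Unrelated or Unlikely, not stable | Released | Followed |
| Grade 2 or higher, Possibly or above, not stable | Followed | Followed |
| As the row above, later reduced to Grade 1 but neither resolved nor stable | Released | Followed |
| Grade 2 or higher, Possibly or above, stable at that grade | Followed | May end |
| Grade 1, or Grade 2 or higher and Unrelated or Unlikely; stable | Released | May end |

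1. **Rows 1, 2 and 4 are the conflict.** Section 8.2 releases the patient and the other passages keep the patient.
2. **Row 5 runs the other way.** Section 8.2 asks for more than the other passages, which breaches none of them.
3. **Row 6 shows no conflict.** Once the event is stable, all the rules allow release.
4. **Illustration of row 2.** Appendix B describes a Grade 3 headache as "unrelenting and severe". If one is present at 12 months, is non-serious, has not reached a stable endpoint and is judged Unlikely, 8.2 lets the patient go and 16.2 does not.
5. **The word therapy.** Section 8.2 does not define it. Section 16.4 collects separate attributions to product and to procedure, and section 2.4.1 describes SB623 as a cell therapy. If the word covers both product and procedure, the table stands as written. If it means the product alone, an unstable Grade 2 or higher event attributed only to the surgery would also be released.
6. **Strength of the wording.** The synopsis says patients will be followed, 16.2 says must, and 16.6 says should. The firm conflict is with the synopsis and 16.2; 16.6 points the same way.

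**The case against.** **Participation is not the same thing as adverse-event follow-up.** This would reconcile 8.2 with section 16, but not with the synopsis, whose entry is also on duration of participation and gives the wider rule.

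**Section 16.2 itself stops at 12 months.** That limit is on the reporting period. The follow-up sentence comes separately and has no time limit.

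**Section 16.2 is the dedicated adverse-event section and is mandatory, so a site complying with the whole protocol already follows these patients.** This stands in part. It is a reason to treat the matter as an inconsistency and not as a missing safeguard. But nothing says that 16.2 overrides 8.2.

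**Many lingering events will already be stable.** This stands and narrows the point. A persistent Grade 1 event, or even an unrelenting headache, may count as a stable clinical endpoint, and then every rule permits release. The conflict covers only events that are neither resolved nor stable.

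**Following related events down to Grade 1 is simply stricter than 16.2.** A reader might infer that this clause can only add protection. It does so for an event stable at Grade 2 or higher. It does not for an event that has dropped to Grade 1 and is still changing, which 8.2 releases and 16.2 keeps.

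**Serious events are covered elsewhere.** Sections 8.1 and 14.0 send every serious event to the DSMB regardless of attribution. This stands as partial protection: review is not follow-up, but the remaining exposure is mainly to non-serious events.

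**The recording rule in 16.3 is breached too.** A reader might infer this, but that rule governs recording. It shows the same unfiltered intent and is not a further conflict.

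**Conclusion.** The inconsistency is real and should be corrected. For adverse events neither resolved nor stable at 12 months, 8.2 releases patients whom the synopsis and 16.2 keep, in the three situations of rows 1, 2 and 4 above. This rests on the plain wording and on no numerical assumption.

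Its size in patients is unknown, because the documents give no rate of events unresolved at 12 months. A reader might be tempted to count grade-by-attribution combinations and report the released share as a magnitude. The documents do not support that. The general four-grade scale in Appendix B applies only to abnormalities not found elsewhere in the WHO table; within the table, headache has no Grade 4 entry and bilirubin no Grade 1. The count would also change with the undefined word in 8.2, it would ignore the stable-endpoint condition, and categories of a rule are not patients.

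Nor should a reader infer damage to the trial's main results. Efficacy, sample size and the incidence of treatment-emergent events, which depends on onset or worsening, are not affected. The consequence is limited to safety follow-up after 12 months, mainly of non-serious events and their recorded outcomes.

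**What to change.** Replace the exception in 8.2 with the general rule, for example: *Participation lasts twelve months after surgery; a patient who then has any unresolved adverse event, whatever its grade or attribution, remains in follow-up until the event resolves or reaches a stable clinical endpoint.* This matches the synopsis, 16.2 and 16.6.

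If the sponsor wants to keep the Grade 1 target for related events of Grade 2 or higher, state it as an additional duty that does not shorten the general rule, and say whether therapy includes the surgical procedure.

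The cost is a reworded sentence, no new scheduled visit, and some additional open events to track after 12 months, in a number that cannot be estimated from the documents.

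A separate, minor wording point can be settled in the same amendment: 16.2 ends the reporting period relative to administration of SB623, which gives sham patients no literal end date. Counting from study surgery, implant or sham, would cover both groups.

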³ Screening eligibility is confirmed at the blinded site, and the surgical safety (i.e. ability to proceed safely with surgery) is confirmed at the unblinded site.

⁵ Only for women of childbearing potential.

SanBio, Inc.

Confidential and Proprietary

Study Period	Screening	Baseline ¹	Sham or Cell Admin	Follow-Up Period				
Study Visit	1	2	3	4	5	6	7	8
Study Day	-84 to -15	-14 to -1	1	2	8 (± 1)	28 (± 7)	84 (± 7)	168 (± 7)
Study Week					1	4	12	24
Study Month						1	3	6
ImagingHead MRI ⁹	X ¹¹	\mathbf{X}^{11}	\mathbf{X}^{10}	X	\mathbf{X}^{11}	\mathbf{X}^{11}		X
Imaging – Diffusion Tensor & Dynamic Susceptibility Contrast Imaging ¹²		Х				Х		X
Clinical TBI Evaluations	X ¹³	\mathbf{X}^{14}				X^{14}	X ¹⁴	X ¹⁴
Global Rating of Perceived Change (subject and clinician)						X ¹⁵	X ¹⁵	X ¹⁵
Serum for anti-HLA Antibodies		Х			X	Х	Х	X
PBMC Sample ¹⁶		Х			Х	Х	Х	X
Adverse Events		Х	X	X	Х	Х	Х	Х
Concomitant Medications	X	Х	X	X	Х	Х	Х	Х
Sham Surgery or Cell Administration ¹⁷			Х					

⁹ Magnetic Resonance Imaging (MRI) of the brain will be obtained using either a 1.5 or 3 Tesla MRI scanner. Each subject should have all scans conducted on the same scanner if possible (excepting those used for stereotactic planning and post-operative assessments, within 2 weeks of the surgery (implant/sham)). T1 and dual echo and FLAIR MRI will be obtained, and will be recorded in standard digital format for review.

¹⁰ Or CT overlaid with MRI from Baseline.

¹¹ MRI with Gadolinium.

¹² Diffusion tensor imaging (DTI) is an MRI technique which characterizes the magnitude, anisotropy and orientation of the diffusion tensor, using the pulsedgradient, spin echo pulse sequence with a single-shot, echo planar imaging readout. Whole brain DTI data will be obtained with at least 30 diffusion encoding directions and may be obtained using either a 1.5 or 3 Tesla MRI scanner. Dynamic Susceptibility Contrast (DSC) Imaging is acquired using single shot gradient echo planar image covering the whole brain. This allows calculation of perfusion parameters.

¹³ GOS-E; Motricity Index

¹⁴ Fugl-Meyer Motor Score; Disability Rating Scale, Action Research Arm Test, Gait Velocity, and NeuroQOL (2 Domains). Primary and secondary efficacy assessments will be completed solely by blinded study personnel (i.e. assessment site efficacy assessor) that do not have access to patient study safety information (this includes adverse events, concomitant medications, progress notes, MRI reports, etc.).

¹⁵ Clinician ideally includes assessment site efficacy assessor who does not have access to patient study safety information because Global Rating of Perceive Change is a component of secondary endpoint, thereby maintaining the blind of the trial.

¹⁶ At each time point that serum antibody samples are collected, an additional sample for PBMC will also be collected and stored at the central laboratory

¹⁷ Subjects can be admitted to the clinical site on Day -1 and undergo study surgical procedure on Day 1 only after all other procedures for this visit have been completed. Subjects will be discharged on Day 2 unless complications or local standard medical practice require a longer stay.

Protocol TBI-01 Version 5, May 17, 2018

SanBio, Inc. Schedule of Assessments (Continued)

Confidential and Proprietary

Study Period	Follow-Up Period				
Study Visit	9	10 ¹⁸			
Study Day	252 (± 14)	336 (± 14)			
Study Week	36	48			
Study Month	9	12			
Informed Consent					
Demographics					
Inclusion/Exclusion					
Eligibility Criteria Review					
Randomization					
Medical History					
Physical Therapy Instruction and Subject Exercise Diary given to subject					
Subject Exercise Diary Review					
Leg Activity Monitor data download ⁴	X	Х			
Pregnancy Test ^{5,6}		Х			
Physical Exam.		Х			
Vital Signs	X	Х			
Chest X-Ray and ECG		Х			
Hematology	X	Х			
Serum Chemistry	X	Х			
INR and APTT		X			
HLA typing of each subject					
ApoE4 & BDNF Val66Met genotyping					
Occult Malignancy					
CESD-R Scale					
Head CT					
ImagingHead MRI ⁹		X ¹¹			
Imaging – Diffusion Tensor & Dynamic Susceptibility Contrast Imaging ¹²		Х			
Clinical TBI Evaluations	X ¹⁴	X ¹⁴			
Global Rating of Perceived Change (subject and clinician)	X ¹⁵	X ¹⁵			
Serum for anti-HLA Antibodies		Х			
PBMC Sample ¹⁶		Х			
Adverse Events	X	X			
Concomitant Medications	X	Х			
Sham Surgery or Cell Administration ¹⁷					

¹⁸ Patients who have withdrawn from the study must return for Visit 10 assessments.

